8.2.4. Clinical Safety Laboratory Assessments

See [Appendix 2](#) for the list of clinical safety laboratory tests to be performed and the [SoA](#) for the timing and frequency.

The investigator must review the laboratory report, document this review, and record any clinically relevant changes occurring during the study in the AE section of the CRF. Clinically significant abnormal laboratory findings are those which are not associated with the underlying disease, unless judged by the investigator to be more severe than expected for the participant's condition.

All laboratory tests with values considered clinically significantly abnormal during participation in the study or within 28 to 35 days after the last dose of study intervention should be repeated until the values return to normal or baseline or are no longer considered clinically significant by the investigator or medical monitor.

If such values do not return to normal/baseline within a period of time judged reasonable by the investigator, the etiology should be identified and the sponsor notified.

All protocol-required laboratory assessments, as defined in [Appendix 2](#), must be conducted in accordance with the laboratory manual and the [SoA](#).

Participants may undergo random urine drug testing at the discretion of the investigator. Drug testing conducted prior to dosing must be negative for participants to receive IP.

8.2.5. Glucometer Monitoring of Glucose

Investigators will monitor fingerstick blood glucose (FSBG) using glucometer measurements in participants with T2DM at the times specified in the [Schedule of Activities](#). FSBG measurements should be taken before breakfast while the participant is confined to the CRU.

FSBG readings will be maintained at the sites in source documents, and only the glucose results from the laboratory will be reported in the study database.

Specifically, if an FSBG result is ≤ 70 mg/dL, a second FSBG should be obtained to confirm the glucose value, in addition to a venous sample that will be sent to the clinical laboratory for confirmation. If the value from this second FSBG is also ≤ 70 mg/dL, the second value will be recorded as a hypoglycemic AE. FSBG will continue to be monitored until the glucose value returns to >70 mg/dL. Samples may be taken more frequently if deemed necessary by the investigator. FSBG readings from a glucometer are permitted at any time if the investigator or participant notes symptoms of hypoglycemia.

8.2.6. Management of Hypoglycemia

Any episode of hypoglycemia must be captured on the HAE CRF. For the definition of a hypoglycemic episode and severity categorization see [Section 8.2.6.1](#) below.

For medical management of hypoglycemia, the investigator may administer oral carbohydrate, glucagon, or IV glucose according to his or her medical judgment. At a minimum however, treatment or administration of a scheduled meal should be given if glucose falls <60 mg/dL for at least 15 minutes, irrespective of whether the participant exhibits symptoms. Investigators may choose to administer treatment sooner if participants have bothersome symptoms of hypoglycemia along with glucose values of ≤ 70 mg/dL.

8.2.6.1. Definition and Severity of Categorization of Hypoglycemic Adverse Event (HAE)

Based on review of the participant on site glucose monitoring, as well as results reported by the central laboratory, the investigator must assess the glucose values as well as any symptoms documented.

HAE is defined as 1 of the following:

1. **Asymptomatic hypoglycemia:** An event not accompanied by typical symptoms of HAE but a plasma glucose value of ≤ 70 mg/dL (3.9 mmol/L) using glucometer (or sponsor-identified central laboratory).
2. **Documented symptomatic hypoglycemia:** An event during which typical symptoms of HAE are accompanied with a glucose value of ≤ 70 mg/dL (3.9 mmol/L) using glucometer (or sponsor-identified central laboratory) and the clinical picture includes prompt resolution with food intake, subcutaneous glucagon, or intravenous (IV) glucose.
3. **Probable symptomatic hypoglycemia:** An event during which symptoms of HAE are *not* accompanied by a plasma glucose determination but was presumably caused by a plasma glucose concentration of ≤ 70 mg/dL (3.9 mmol/L), and the clinical picture includes prompt resolution with food intake, subcutaneous glucagon, or IV glucose.

Each episode of HAE must be categorized with respect to severity. To characterize the event as severe, all 3 criteria below must be met:

1. The participant exhibits altered mental and/or physical functioning that requires assistance from another person for recovery.
2. The participants exhibit at least 1 of the following neurological symptoms:
 - Memory loss;
 - Confusion;
 - Uncontrolled behavior;
 - Irrational behavior;
 - Unusual difficulty in awakening;
 - Suspected seizure;
 - Seizure;
 - Loss of consciousness.
3. Either:
 - If blood glucose was measured and was ≤ 54 mg/dL (2.7 mmol/L) using glucometer (or central laboratory); or
 - If blood glucose was not measured, the clinical manifestations were reversed by oral carbohydrates, subcutaneous glucagon, or intravenous glucose.

Events that do not meet all criteria above for severe HAE should be characterized as mild or moderate in severity.

Any episode of HAE must be captured on the HAE CRF.

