2.2.4.1. Clinical Safety

Clinical data from the completed C3421001, C3421002, and C3421003 studies are provided in the IB for PF-06882961.

In study C3421002, PF-06882961 doses ranging from 10 mg BID to 120 mg BID were generally safe and well tolerated. A total of 98 participants with T2DM on a background of metformin were randomized to receive PF-06882961 or matching placebo in a 3:1 randomization ratio, and 92 participants completed the study. Six participants discontinued from the study, of which 2 discontinuations were due to treatment-related TEAEs, and 4 withdrew during the treatment or follow-up period for non-treatment related reasons.

A total of 319 all-causality treatment-emergent adverse events (TEAEs) were reported in these participants, of which a majority (294 or 92%) were mild in intensity, 23 (or 7%) were moderate, and 2 (or 1%) were severe in intensity.

The total number of TEAEs generally increased with higher daily doses of PF-06882961. The most frequently reported TEAEs (by number of occurrences) in these cohorts have been nausea (48), dyspepsia (32), vomiting (26), diarrhea (24), headache (23), constipation (20), and decreased appetite (19). In addition, there was one symptomatic hypoglycemic AE reported in 1 participant in the 120 mg BID group. This AE was non-fasting, mild in severity, and of limited duration (15 minutes). No deaths occurred in the C3421002 study. Two participants experienced 2 severe TEAEs during the study, 1 of which occurred in the dosing period and was considered treatment related, the other occurred during the follow-up period and was not considered treatment related. One participant experienced 2 non-treatment-related SAEs, 1 of which occurred in the follow-up period and the other occurred outside of the study reporting period.

In C3421002, there were isolated values for laboratory tests, vital signs and ECG intervals outside of the reference ranges; however, no clear adverse trends were apparent in these parameters. As has been reported for marketed GLP-1R agonists¹¹ increases in heart rate were observed, with mean increases ranging from 5 to 15 beats per minute (bpm) across doses administered, and with most heart rate values within the normal range.

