15. Known prior participation in a trial involving PF-06882961 or known hypersensitivity or intolerance to a GLP-1R agonist.

Diagnostic Assessments:

16. Screening standard 12-lead ECG that demonstrates a clinically relevant abnormality that requires further diagnostic evaluation or intervention (eg, new, clinically relevant arrhythmia, conduction disturbance, findings suggestive of ischemia). A potential participant whose pre-dose ECG (on Day 1, 0 hour) demonstrates a clinically relevant abnormality that requires further diagnostic evaluation or intervention will be considered a screen failure.

17. A positive COVID-19 test in the screening period.
18. A positive urine drug test (or other type of drug test in anuric participants on dialysis only).
 - **Note:** Participants who have been medically prescribed opiates/opioids, benzodiazepines or marijuana and report the use of these drugs to the investigator at Screening may be eligible to participate with sponsor approval. Use of marijuana during inpatient stay is prohibited.
19. Participants with ANY of the following abnormalities in clinical laboratory tests at Screening, as assessed by the study specific central laboratory and confirmed by a single repeat test, if deemed necessary:
 - Aspartate aminotransferase (AST) or alanine aminotransferase (ALT) level $\geq 2 \times$ upper limit of normal (ULN);
 - Total bilirubin level $\geq 1.5 \times$ ULN; participants with a history of Gilbert's syndrome may have direct bilirubin measured and would be eligible for this study provided the direct bilirubin level is \leq ULN.
 - Fasting C-peptide < 0.8 ng/mL.
 - Fasting plasma glucose (FPG) > 270 mg/dL (15 mmol/L) at screening (S1).

Other Exclusions:

20. History of regular alcohol consumption exceeding 7 drinks/week for female participants or 14 drinks/week for male participants (1 drink = 5 ounces [150 mL] of wine or 12 ounces [360 mL] of beer or 1.5 ounces [45 mL] of hard liquor) within 6 months before screening.
21. Blood donation (excluding plasma donations) of approximately 1 pint (500 mL) or more within 60 days prior to dosing.
22. History of sensitivity to heparin or heparin-induced thrombocytopenia **only if** heparin is planned to flush intravenous catheters.
23. Unwilling or unable to comply with the criteria in the [Lifestyle Considerations](#) section of the protocol.

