8.2.7. Management of Hyperglycemia

Hyperglycemia is defined as the following:

- Fasting plasma glucose ≥ 270 mg/dL (15.0 mmol/L) using glucometer (or central laboratory).

The investigator should determine if the participant collected the samples after an adequate fasting period; and if the participant is following recommended dietary guidelines. Proper dietary and collection procedures should be reinforced with the participant.

A participant with hyperglycemia should receive treatment at the discretion of the investigator (see [Section 6.5](#)).

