The investigator will make an assessment of intensity for each AE and SAE reported during the study and assign it to 1 of the following categories:

- Mild: An event that is easily tolerated by the participant, causing minimal discomfort and not interfering with everyday activities.
- Moderate: An event that causes sufficient discomfort and interferes with normal everyday activities.
- Severe: An event that prevents normal everyday activities. An AE that is assessed as severe should not be confused with an SAE. Severe is a category utilized for rating the intensity of an event; and both AEs and SAEs can be assessed as severe.
- An event is defined as “serious” when it meets at least 1 of the predefined outcomes as described in the definition of an SAE, NOT when it is rated as severe.

Assessment of Causality

- The investigator is obligated to assess the relationship between study intervention and each occurrence of each AE/SAE.
- A “reasonable possibility” of a relationship conveys that there are facts, evidence, and/or arguments to suggest a causal relationship, rather than a relationship cannot be ruled out.
- The investigator will use clinical judgment to determine the relationship.
- Alternative causes, such as underlying disease(s), concomitant therapy, and other risk factors, as well as the temporal relationship of the event to study intervention administration will be considered and investigated.
- The investigator will also consult the Investigator’s Brochure (IB) and/or product information, for marketed products, in his/her assessment.
- For each AE/SAE, the investigator **must** document in the medical notes that he/she has reviewed the AE/SAE and has provided an assessment of causality.
- There may be situations in which an SAE has occurred and the investigator has minimal information to include in the initial report to the sponsor. However, **it is very important that the investigator always make an assessment of causality for every event before the initial transmission of the SAE data to the sponsor.**
- The investigator may change his/her opinion of causality in light of follow-up information and send an SAE follow-up report with the updated causality assessment.
- The causality assessment is one of the criteria used when determining regulatory

reporting requirements.

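### The glucose cut-off for a severe hypoglycemic adverse event is misconverted: 54 mg/dL is 3.0 mmol/L, not 2.7 mmol/L

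*Protocol*

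**What the plan says.** Protocol Section 8.2.6.1 requires every HAE to be graded for severity. A severe grade needs three things together: impaired functioning that requires another person's help, at least one listed neurological symptom, and a third criterion. When glucose was measured, the third criterion is a value at or below "54 mg/dL (2.7 mmol/L) using glucometer (or central laboratory"). When it was not measured, reversal of the clinical signs by carbohydrate, glucagon or intravenous glucose takes its place. The section closes the rule with "Events that do not meet all criteria above for severe HAE should be characterized as mild or moderate in severity".

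Glucose appears in both units in three other places:

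- Section 8.2.6.1, asymptomatic and documented symptomatic HAE: "70 mg/dL (3.9 mmol/L) using glucometer (or sponsor-identified central laboratory"). The same pair of values is given for probable symptomatic HAE.
- Section 8.2.7, definition of hyperglycemia: "270 mg/dL (15.0 mmol/L) using glucometer (or central laboratory").
- Section 5.2.1, exclusion 19: "270 mg/dL (15 mmol/L) at screening (S1").

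Neither the protocol nor the SAP restates or corrects the 54 mg/dL threshold anywhere else.

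**The concern.** A threshold printed in two units should describe one concentration, and this one describes two. The line is a working decision rule, not background text: when glucose was measured and the first two criteria are met, this cut-off alone decides between severe and not severe.

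Take a participant who needed help, was confused, and had a glucose of 52 mg/dL. That event is severe by the mg/dL figure. In mmol/L the reading is 2.9, above the printed 2.7, so the event becomes mild or moderate. Using the mmol/L figure therefore under-grades, which is the less safe direction. Incidence and severity of treatment-emergent adverse events is a secondary endpoint (Protocol Section 3), and in a study of about 40 participants one misgraded severe event would be noticeable.

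**Working it through.** **Inputs.** The glucose pairs come from Protocol Sections 5.2.1, 8.2.6.1 and 8.2.7. As an outside check I also use the molar mass of glucose, about 180.16 g/mol. This is a physical constant that the documents do not give; it makes the factor 18.016.

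**Formula.** mmol/L = (mg/dL) / F, so F = (mg/dL) / (mmol/L).

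**Step 1: the factor implied by each pair.** The range allows for rounding of the mmol/L figure to one decimal.

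| Pair | Implied F | Range |
|---|---|---|
| 70 mg/dL, 3.9 mmol/L | 70/3.9 = 17.95 | 70/3.95 to 70/3.85 = 17.72 to 18.18 |
| 270 mg/dL, 15.0 mmol/L | 270/15.0 = 18.00 | 270/15.05 to 270/14.95 = 17.94 to 18.06 |
| 54 mg/dL, 2.7 mmol/L | 54/2.7 = 20.00 | 54/2.75 to 54/2.65 = 19.64 to 20.38 |

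The first two ranges overlap each other and contain 18.016. The third overlaps neither, so rounding cannot reconcile it.

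**Step 2: try to reproduce the stated 2.7 mmol/L.**

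- F = 17.95: 54/17.95 = 3.01
- F = 18.00: 54/18.00 = 3.00
- F = 18.016: 54/18.016 = 2.997

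All three round to 3.0, so the stated figure is not reproduced. The same method does reproduce the other pairs: 70/18.016 = 3.89, which rounds to 3.9, and 270/18.016 = 14.99, which rounds to 15.0.

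**Step 3: what 2.7 mmol/L means in mg/dL.** 2.7 × 18.0 = 48.6 mg/dL. Values from about 47.7 (2.65 × 18.016) to 49.5 mg/dL (2.75 × 18.016) round to 2.7. A value of 54 lies well outside that range.

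**Step 4: the size of the gap.** 3.0 − 2.7 = 0.3 mmol/L. In mg/dL, 54 − 48.6 = 5.4, and 5.4/54 = 10%.

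**Step 5: which readings change grade** (F = 18.016, criteria 1 and 2 met).

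| mg/dL | mmol/L | To one decimal | At or below 54 mg/dL? | At or below 2.7 mmol/L, one decimal? |
|---|---|---|---|---|
| 48 | 2.66 | 2.7 | yes | yes |
| 49 | 2.72 | 2.7 | yes | yes |
| 50 | 2.78 | 2.8 | yes | no |
| 51 | 2.83 | 2.8 | yes | no |
| 52 | 2.89 | 2.9 | yes | no |
| 53 | 2.94 | 2.9 | yes | no |
| 54 | 3.00 | 3.0 | yes | no |

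With mmol/L read to one decimal, the whole-number readings that change grade are 50 to 54 mg/dL. If mmol/L is not rounded, 49 mg/dL (2.72) changes as well.

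**The case against.** The best case on the other side accepts the arithmetic and disputes the weight.

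- **No site is known to work in mmol/L.** Monitoring (Section 8.2.5) and the treatment levels (Section 8.2.6) are in mg/dL only, and mg/dL leads in every dual-unit pair. A reader who uses the leading unit grades correctly. This stands: the harm depends on an assumption.
- **The window is narrow and events are rare.** The participant must meet both other criteria, have a measured glucose in a band of about 5 mg/dL, and be graded in mmol/L. In the 28-day study, with 98 participants randomized and doses up to 120 mg twice daily on metformin, "there was one symptomatic hypoglycemic AE reported in 1 participant in the 120 mg BID group" (Section 2.2.4.1), and it was mild. Here each participant gets one 20 mg dose. This stands too, although insulin is allowed, including sliding-scale dosing in the unit (Section 6.5), so the count is not certain to be zero.
- **Care and safety reporting do not depend on it.** Section 8.2.6 says that "treatment or administration of a scheduled meal should be given if glucose falls" below 60 mg/dL for at least 15 minutes, and allows earlier treatment for symptoms at or below 70 mg/dL. Both levels are above the disputed band. The general intensity scale in Section 10.3.3 is functional ("Severe: An event that prevents normal everyday activities"), and seriousness is judged by outcome and medical importance. This stands.
- **No specified analysis uses the cut-off.** The SAP's safety sections do not mention HAE severity. This stands.

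One technical defense is a conversion between whole blood and plasma. With an assumed ratio of 1.11, which is not in the documents, 54/18.016/1.11 = 2.70. That does not rescue the line. The protocol states no such adjustment and applies the cut-off to the glucometer and the central laboratory alike. The same adjustment would also turn 70 mg/dL into 70/18.016/1.11 = 3.5 mmol/L, not the printed 3.9.

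These points limit the consequence. They do not make the line correct.

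**Conclusion.** The error is real and certain on the protocol's own conversion: the two halves of the threshold differ by 0.3 mmol/L (5.4 mg/dL, 10%). It should be corrected because it sits in a rule that must give one grade for one blood sample.

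The practical effect is small and confined to the severity category on the HAE CRF. It arises only if someone grades in mmol/L (an assumption) and an event meets the first two criteria with a measured glucose of 50 to 54 mg/dL. Very few such events are expected, possibly none.

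The documents do not say which unit was intended. That mg/dL governs is an inference from its leading position and from its use alone in Sections 8.2.5 and 8.2.6. It makes the figure in parentheses the likely mistake.

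**What to change.** In Protocol Section 8.2.6.1, third criterion for a severe HAE, change 2.7 mmol/L to 3.0 mmol/L and keep 54 mg/dL.

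If the sponsor's clinicians confirm that 2.7 mmol/L was meant, change the mg/dL value to 49 instead. That pair agrees at one decimal (49/18.016 = 2.72), the same precision as 70 mg/dL with 3.9 mmol/L. In that case the protocol should also say that mmol/L values are read to one decimal.

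Use the same single threshold in the HAE CRF instructions. They are not among the documents, so whether they carry the wrong figure needs checking.

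The cost is one number in one line, plus that check. Design, sample size and analysis do not change.

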8.2.7. Management of Hyperglycemia

Hyperglycemia is defined as the following:

- Fasting plasma glucose ≥ 270 mg/dL (15.0 mmol/L) using glucometer (or central laboratory).

The investigator should determine if the participant collected the samples after an adequate fasting period; and if the participant is following recommended dietary guidelines. Proper dietary and collection procedures should be reinforced with the participant.

A participant with hyperglycemia should receive treatment at the discretion of the investigator (see [Section 6.5](#)).

8.2.8. Pregnancy Testing

Pregnancy tests will be both urine and serum tests, and must have a sensitivity of at least 25 mIU/mL. Pregnancy tests will be performed in WOCBP at the times listed in the [SoA](#). Following a negative pregnancy test result at screening (S1 and S2), appropriate contraception must be commenced/continued and a second negative pregnancy test result will be required prior the participant's receiving the IP. Pregnancy tests will also be done whenever 1 menstrual cycle is missed during the active treatment period (or when potential pregnancy is otherwise suspected). Pregnancy tests may also be repeated if requested by Institutional Review Boards (IRBs)/ethics committees (ECs) or if required by local regulations.

8.2.9. COVID-19 Specific Assessments

Participants will be pre-screened for COVID-19 related symptoms and risks^{26,27} and tested for SARS-CoV-2 infection using a locally approved test at the timepoints specified in the [SoA](#). Additional testing may be conducted as required by local regulations or by the Principal Investigator. Results must be negative for admission to the CRU.

8.3. Adverse Events and Serious Adverse Events

The definitions of an AE and an SAE can be found in [Appendix 3](#).

AEs will be reported by the participant (or, when appropriate, by a caregiver, surrogate, or the participant's legally authorized representative).

The investigator and any qualified designees are responsible for detecting, documenting, and recording events that meet the definition of an AE or SAE and remain responsible to pursue and obtain adequate information both to determine the outcome and to assess whether it meets the criteria for classification as an SAE or that caused the participant to discontinue the study (see [Section 7](#)).

In addition, the investigator may be requested by Pfizer Safety to obtain specific follow-up information in an expedited fashion.

8.3.1. Time Period and Frequency for Collecting AE and SAE Information

The time period for actively eliciting and collecting AEs and SAEs (“active collection period”) for each participant begins from the time the participant provides informed consent, which is obtained before the participant’s participation in the study (ie, before undergoing any study-related procedure and/or receiving study intervention), through and including a minimum of 28 calendar days, except as indicated below, after the last administration of the study intervention.

Follow-up by the investigator continues throughout and after the active collection period and until the AE or SAE or its sequelae resolve or stabilize at a level acceptable to the investigator and Pfizer concurs with that assessment.

For participants who are screen failures, the active collection period ends when screen failure status is determined.

If the participant withdraws from the study and also withdraws consent for the collection of future information, the active collection period ends when consent is withdrawn.

If a participant definitively discontinues or temporarily discontinues study intervention because of an AE or SAE, the AE or SAE must be recorded on the CRF and the SAE reported using the CT SAE Report Form.

Investigators are not obligated to actively seek AE or SAE after the participant has concluded study participation. However, if the investigator learns of any SAE, including a death, at any time after a participant has completed the study, and he/she considers the event to be reasonably related to the study intervention, the investigator must promptly report the SAE to Pfizer using the CT SAE Report Form.

